**9.3.1 Exposures**

Not applicable.

We defined four groups (group A-D) according to the diagnosis and laboratory measurements. The group A and group B included all diabetic patients with/without established CV disease, CKD, or at high CV risk, respectively. The group C included all non-diabetic patients with established cardiovascular disease, chronic kidney disease, or at high cardiovascular risk. The group D included non-diabetic patients without established cardiovascular disease, chronic kidney disease, and not at high cardiovascular risk. For group D, we will randomly sample study populations to acquire a 1:1 sample of non-diabetic patients without disease by matching on age and gender with group A.

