6. RESEARCH METHODS

6.1 STUDY DESIGN

This study is an observational, cross-sectional study based on a routinely collected database. We constructed four groups for comparison: the group A and group B included all diabetic patients with/without established CV disease, CKD, or at high CV risk, respectively. The group C included all non-diabetic patients with established cardiovascular disease, chronic kidney disease, or at high cardiovascular risk. The group D will be constructed to match group A, non-diabetic patients will be included without established cardiovascular disease, chronic kidney disease, and not at high cardiovascular risk. For group D, we will randomly sample study populations to acquire a 1:1 sample of non-diabetic patients without disease by matching on age and gender with group A.

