7.2.2 Secondary outcomes

- 1) The demographic characteristics of the latest visit for all patients, as well as the trends for inpatients over time (2015, 2017, and 2019 respectively). Clinical characteristics of outpatients and hospitalized patients will be described respectively.

Table 2. The demographic and clinical characteristics of the latest visit

| Outpatients | | | | Inpatients | | | | Total patients |
|--|----------------|----------------|----------------|-------------------|----------------|----------------|----------------|-----------------------|
| Group A | Group B | Group C | Group D | Group A | Group B | Group C | Group D | |
| Demographic characteristics in 2015 | | | | | | | | |
| Age (mean, sd) | | | | | | | | |
| Gender (n, %) | | | | | | | | |
| Insurance payment (n, %) | | | | | | | | |
| Demographic characteristics in 2017 | | | | | | | | |
| Age (mean, sd) | | | | | | | | |
| Gender (n, %) | | | | | | | | |
| Insurance payment (n, %) | | | | | | | | |
| Demographic characteristics in 2019 | | | | | | | | |
| Age (mean, sd) | | | | | | | | |
| Gender (n, %) | | | | | | | | |
| Insurance payment (n, %) | | | | | | | | |

Note Group A Diabetes with cardiovascular disease, chronic kidney disease or at high cardiovascular risk; Group B Diabetes without cardiovascular disease, chronic kidney disease or at high cardiovascular risk; Group C Non-diabetes with cardiovascular disease, chronic kidney disease or at high cardiovascular risk; Group D Non-diabetes without cardiovascular disease, chronic kidney disease or at high cardiovascular risk;

2) The clinical characteristics of the studied population of the latest visit for all patients, as well as the trends for inpatients over time (2015, 2017, and 2019 respectively). Clinical characteristics of outpatients and hospitalized patients will be described respectively.

Table 3. The clinical characteristics of the latest visit

| Outpatients | | | | Inpatients | | | | Total patients |
|---|----------------|----------------|----------------|-------------------|----------------|----------------|----------------|-----------------------|
| Group A | Group B | Group C | Group D | Group A | Group B | Group C | Group D | |
| Clinical characteristics in 2015 | | | | | | | | |
| Department of discharge | | | | | | | | |
| Death | | | | | | | | |
| Clinical characteristics in 2017 | | | | | | | | |
| Department of discharge | | | | | | | | |
| Death | | | | | | | | |

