| Clinical characteristics in 2019 | | | | | | | | |
| Department of discharge | | | | | | | | |
| Death | | | | | | | | |

Table 4. The laboratory measurement of the latest visit

| Outpatients | | | | Inpatients | | | | Total patients |
|--------------------|----------------|----------------|----------------|-------------------|----------------|----------------|----------------|-----------------------|
| Group A | Group B | Group C | Group D | Group A | Group B | Group C | Group D | |
| | | | | | | | | |
| | | | | | | | | |

Clinical characteristics in 2015

HbA1c
Random blood glucose
Serum creatinine

[figure not shown]
Clinical characteristics in 2017

[figure not shown]
HbA1c
Random blood glucose
Serum creatinine

Clinical characteristics in 2019

HbA1c
Random blood glucose
Serum creatinine

Note Group A Diabetes with cardiovascular disease, chronic kidney disease or at high cardiovascular risk; Group B Diabetes without cardiovascular disease, chronic kidney disease or at high cardiovascular risk; Group C Non-diabetes with cardiovascular disease, chronic kidney disease or at high cardiovascular risk; Group D Non-diabetes without cardiovascular disease, chronic kidney disease or at high cardiovascular risk;

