7.3 Covariates

No applicable. This is a cross-sectional study aiming to describe the proportion, clinical characteristics and economic burden.

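### Group D is matched to Group A on age and gender over the whole sample, but SAP Tables 2-4 show the two groups only within setting and calendar year, where the design does not preserve that balance

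*SAP*

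**What the plan says.** **Matching.** SAP 6.1 introduces the design with "We constructed four groups for comparison" and then samples Group D at random, 1:1, "by matching on age and gender with group A". Protocol 9.3.1 repeats this: the aim is to "acquire a 1:1 sample of non-diabetic patients without disease by matching on age and gender with group A". Neither document lists setting, calendar year or visit as a matching variable, and neither says at what date age is taken for the match.

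**Display.** SAP 7.2.2 states "Clinical characteristics of outpatients and hospitalized patients will be described respectively". Tables 2, 3 and 4 accordingly carry Groups A to D under an outpatient heading and again under an inpatient heading. Each table has row blocks by year, such as "Demographic characteristics in 2015" in Table 2 and "Clinical characteristics in 2019" in Table 3. The only pooled column is the total over all patients, which is not split by group. Table 1, the primary outcome table, has rows for A and C only.

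**Text and shells.** The outcome text is looser than the shells. It asks for the latest visit for all patients, "as well as the trends for inpatients over time (2015, 2017, and 2019 respectively"), so it names year trends for inpatients only. The shells show the three years for both settings.

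**Adjustment.** SAP 7.3 on covariates reads "No applicable. This is a cross-sectional study aiming to describe the proportion, clinical characteristics and economic burden". SAP 10.1 plans t tests, analysis of variance, chi-square and rank tests at a two-sided 0.05 level. It names no stratified, standardised or matched-pair method.

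**The concern.** Matching on age and gender makes A and D alike in those two variables over all matched pairs. It does not make them alike within a subset, unless membership of the subset depends on age and gender in the same way in both groups. Here the subsets are setting and year.

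There is reason to doubt that condition. Group A has diabetes plus cardiovascular disease, heart failure, chronic kidney disease or high cardiovascular risk, and Group D has none of these, so the reasons for admission are likely to differ. The diagnostic definitions also depend on setting: for most conditions one discharge diagnosis qualifies a patient but two outpatient diagnoses are needed. Setting is thus tied to group membership.

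At stake is how the A and D columns of Tables 3 and 4 (death, HbA1c, random glucose, serum creatinine) are read. A reader told that D is matched to A will take the columns as comparable in age and gender, although nothing in the plan secures that cell by cell.

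**Working it through.** **1. Inputs.** The documents give no inpatient share, no age distribution and no size for Groups A to D, so there is no planned figure to reproduce. Every numerical input below is an assumption.

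**2. Condition for balance.** Let matched pairs share an age density f(x), and let pA(x) and pD(x) be the probabilities of being an inpatient at age x. The inpatient mean ages are

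- A: ∫ x f(x) pA(x) dx / ∫ f(x) pA(x) dx
- D: ∫ x f(x) pD(x) dx / ∫ f(x) pD(x) dx

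These are equal if pA is proportional to pD at every age. Equal odds ratios for age are not enough when the overall inpatient shares differ. The same argument holds for gender and for calendar year.

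**3. First set of assumptions.** Age has mean 64 and SD 11 in both groups. The log-odds of being an inpatient are 0 + 0.05(x - 64) in A, so 50% of A are inpatients. In D they are -1.5 + s(x - 64), so about 18% to 20% of D are inpatients.

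| Age slope s in D | Inpatient mean age, A | Inpatient mean age, D | Inpatient gap, A - D | Outpatient gap, A - D |
|---|---|---|---|---|
| 0.05 (as in A) | 66.8 | 68.6 | -1.8 | -1.7 |
| 0.02 | 66.8 | 66.0 | +0.9 | -2.4 |
| 0 | 66.8 | 64.0 | +2.8 | -2.8 |
| -0.02 | 66.8 | 62.0 | +4.8 | -3.3 |
| same model as A (50% inpatient) | 66.8 | 66.8 | 0.0 | 0.0 |

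In SD units of age the inpatient gaps run from 0.9/11 = 0.08 to 4.8/11 = 0.44.

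**4. Second set of assumptions.** Age has mean 65 and SD 11; about 50% of A and 20% to 22% of D are inpatients. Slopes are log-odds per 10 years.

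| Slope in A | Slope in D | Inpatient gap | Outpatient gap |
|---|---|---|---|
| 0.4 | 0.4 | -1.4 | -1.3 |
| 0.4 | 0 | +2.3 | -2.3 |
| 0.4 | -0.3 | +5.1 | -3.0 |
| 0.2 | 0.6 | -4.1 | +0.3 |

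With the same admission model in both groups the gap is again about 0. Adding opposite gender effects of 0.3 on the log-odds scale to the second row puts the gender share 9.3 points apart in inpatients and 5.1 points apart, in the other direction, in outpatients.

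**5. Pairs that stay together.** Ignoring any link through age, the share of pairs in the same setting is pA·pD + (1 - pA)(1 - pD). With 50% and 20% inpatients this is 0.5 × 0.2 + 0.5 × 0.8 = 0.50. If each group's visits are spread evenly over five years, the share also in the same year is 5 × 0.2 × 0.2 = 0.20, so 0.50 × 0.20 = 10% of pairs share setting and year. The share falling in one of the three displayed years is 3 × 0.2 × 0.2 = 0.12, giving 0.50 × 0.12 = 6% in a displayed cell. Other assumed shares (30% and 10% inpatients, or A's visits concentrated in later years) give up to 13% and 9%. Broken pairs do not by themselves mean imbalance; they show that the pairing is not what balances the cells.

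**6. Not calculated.** The effect of calendar year on the age gap was not modelled, and no age gap was converted into a bias in death or laboratory values.

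**The case against.** The strongest case on the other side has five parts.

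- **The loss of balance is conditional.** This stands. A reader might infer that the matching fails in every reported cell. The documents do not support that: they give no admission pattern, and with the same pattern in A and D the gap is zero. What can be said is that the design does not secure balance.
- **Size and sign rest on assumptions.** This also stands. The gap changes sign between scenarios, and one of them gives only 0.9 years, so no direction of bias can be claimed.
- **Not all A-D tables are visible.** A reader might infer that every A-D comparison in the study is affected. SAP section 3 promises tables for the further outcomes, and SAP 7.2 names length of stay and hospital cost, but those tables are not in the text available. The point covers Tables 2-4 only.
- **The study is descriptive.** The objectives are to describe, examine and explore, and no A-D test is named: SAP 10.1 refers to subgroups such as age, gender, department and underlying disease. Groups B and C are unmatched in the same tables. This lowers the importance, but it does not remove the point, because the SAP builds a matched comparator for a stated purpose of comparison and plans significance tests without adjustment.
- **The imbalance will be visible.** Table 2 reports age and gender by group in each cell, so a careful reader could detect it. Detecting a gap does not correct the figures in Tables 3 and 4.

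**Conclusion.** The point holds in a limited form. Group D is matched over the whole sample, the visible tables never show A against D in that sample, and nothing in the plan restores age and gender balance in the setting-year cells. How large the imbalance will be, and in which direction, is unknown. The first set of assumptions gives inpatient mean-age gaps of about -2 to +5 years; the second reaches -4.1 when admission rises more steeply with age in D than in A; identical admission patterns give none.

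The consequence is confined to the secondary, descriptive A-D contrasts in Tables 3 and 4. A reader might infer that the study's main result is compromised. It is not: the primary outcome, Table 1, does not use Group D. The change is worth making because it is cheap and restores the comparison that SAP 6.1 sets up.

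**What to change.** 1. Add A and D columns for the full matched sample, at the latest visit, to Tables 2-4. State the date at which age is taken for matching.
2. For A-D contrasts in Tables 3 and 4 within a setting-year cell, standardise D to A's age and gender distribution in that cell. For age-gender stratum j in cell k, each D patient gets the weight (nA,jk / nA,k) / (nD,jk / nD,k). An alternative is to draw D separately within each setting, with age defined at the tabulated visit.
3. Report the standardised difference in age and gender between A and D for each cell, before and after weighting.
4. Label any unweighted setting-year cell as unmatched and descriptive.
5. State whether the year blocks apply to outpatients as well as inpatients, since the text and the shells differ.

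Re-matching within every setting-year cell is possible but less attractive. One patient can contribute visits in both settings and several years, so it would need up to 2 × 3 = 6 separate D samples. Admission may also be a consequence of the diseases that separate A from D, so matching on it changes the contrast.

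The cost is a little more analysis with variables already collected (birthday, sex, admission, discharge and diagnosis dates), and lower precision in cells with few D patients. Weighting repairs age and gender only; it does not make the two groups' reasons for admission alike.

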6.2 SETTING

After considering the availability, feasibility, coverage, number of included population and data integrity, this study is based on Tianjin regional medical database from 01/01/2015 to 31/12/2019.

6.3 STUDY POPULATION

Diabetic/non-diabetic patients with/without established cardiovascular disease, chronic kidney disease, or at high cardiovascular risk.

Inclusion Criteria:

- 1) Patients in the Tianjin regional database from 01/01/2015 to 31/12/2019.
- 2) Group A: patients with diagnosis of diabetes, and with diagnosis of cardiovascular disease, heart failure, chronic kidney disease or at high cardiovascular risk;
- 3) Group B: patients with diagnosis of diabetes, but not with diagnosis of cardiovascular disease, heart failure, chronic kidney disease or at high cardiovascular risk;
- 4) Group C: patients with diagnosis of cardiovascular disease, heart failure, chronic kidney disease or at high cardiovascular risk, but not with diagnosis of diabetes;
- 5) Group D: patients without diagnosis of cardiovascular disease, heart failure, chronic kidney disease or at high cardiovascular risk, and without diagnosis of diabetes. We will randomly select a group of non-diabetic patients without any of the above diseases by matching on age and gender.

Definition of diabetes, cardiovascular disease, chronic kidney disease and high cardiovascular risk

- Diabetes: patients with at least 1 discharged diagnosis or 2 outpatient diagnosis of diabetes (ICD-10 E10-E14)
- Cardiovascular disease: patients with at least 1 discharged diagnosis or 2 outpatient diagnosis of ischemic heart diseases (ICD-10 I20~I25); or patients with at least 1 discharged diagnosis or 2 outpatient diagnosis of cerebrovascular diseases (ICD-10 I60~I69); or patients with at least 1 discharged diagnosis or 2 outpatient diagnosis of ischemic peripheral artery disease (ICD-10 E10.501, E11.603, E14.501, E14.606, E14.503, I73.9, I99.03, I99.04);
- Heart failure: patients with at least 1 discharged diagnosis or 2 outpatient diagnosis of heart failure (ICD-10 I50);
- Chronic kidney disease: inpatients with at least once 1 discharged diagnosis CKD (ICD-10 N18), or inpatients with the last estimated glomerular filtration rate (eGFR, calculated by CKD-EPI equation) <60 mL/min/1.73 m² or prescription of dialysis, but not with the diagnosis of acute kidney injury (ICD-10 N17); or outpatients with at least 2 diagnosis of CKD or with two consecutive eGFR (calculated by CKD-EPI equation) <60 mL/min/1.73 m² by 90 days or more.
- High cardiovascular risk: patients with at least 1 discharged diagnosis or 2 outpatient diagnosis of hypertension (ICD-10 I10~I15); or at least 1 discharged diagnosis or 2 outpatient diagnosis of hyperlipidemia (ICD-10 E78.001-E78.003, E78.101, E78.203, E78.301-E78.304, E78.306, E78.401, E78.501, E78.902)

Exclusion Criteria:

- 1) Patients with non-Chinese nationalities;
- 2) Duplicated storage (records with same inpatient code).

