#### **Inclusion Criteria:**

- 1) Patients in the Tianjin regional database from 01/01/2015 to 31/12/2019.
- 2) Group A: patients with diagnosis of diabetes, and with diagnosis of cardiovascular disease, heart failure, chronic kidney disease or at high cardiovascular risk.
- 3) Group B: patients with diagnosis of diabetes, but not with diagnosis of cardiovascular disease, heart failure, chronic kidney disease or at high cardiovascular risk.
- 4) Group C: patients with diagnosis of cardiovascular disease, heart failure, chronic kidney disease or at high cardiovascular risk, but not with diagnosis of diabetes.
- 5) Group D: patients without diagnosis of cardiovascular disease, heart failure, chronic kidney disease or at high cardiovascular risk, and without diagnosis of diabetes. We will randomly select a group of non-diabetic patients without any of the above diseases by matching on age and gender.

Definition of diabetes, cardiovascular disease, chronic kidney disease and high cardiovascular risk:

- Diabetes: patients with at least 1 discharged diagnosis or 2 outpatient diagnosis of diabetes (the first diagnosis will be the index diagnosis, and the time interval between diagnoses is not restricted) (International classification of disease (ICD)-10 E10-E14)
- Cardiovascular disease: patients with at least 1 discharged diagnosis or 2 outpatient diagnosis of ischemic heart diseases (the first diagnosis will be the index diagnosis, and the time interval between diagnoses is not restricted) (ICD-10 I20~I25); or patients with at least 1 discharged diagnosis or 2 outpatient diagnosis of cerebrovascular diseases (the first diagnosis will be the index diagnosis, and the time interval between diagnoses is not restricted) (ICD-10 I60~I69); or patients with at least 1 discharged diagnosis or 2 outpatient diagnosis of ischemic peripheral artery disease (the first diagnosis will be the index diagnosis, and the time interval between diagnoses is not restricted) (ICD-10 E10.501, E11.603, E14.501, E14.606, E14.503, I73.9, I99.03, I99.04);

- Heart failure: patients with at least 1 discharged diagnosis or 2 outpatient diagnosis of heart failure (the first diagnosis will be the index diagnosis, and the time interval between diagnoses is not restricted) (ICD-10 I50).

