### **9.7.1 Main analysis**

Before analyses start, 200 randomly selected medical chart will be fully reviewed by well-trained experts to validate the accuracy and sensibility of code used to identify patients with cardiovascular disease or at high cardiovascular risk, chronic kidney disease and type 2 diabetes. This QC procedure for database study would be performed by [REDACTED].

The analyses will mainly describe the patient demographic characteristics, comorbidities, treatment pattern and economic burden based on 40 hospitals EMRs of Tianjin regional database. Descriptive data will be provided. The statistical methods and analyses will be described in detail in a Statistical and Epidemiological Analysis Plan (SEAP) prior to the commencement of any analyses.

Characteristics presented as continuous data will be summarized through means, standard deviations, medians, minimum and maximum values, whereas, categorical data will be summarized as counts and proportions.

All tests will be two-sided unless otherwise specified

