7.2.1 Primary outcomes

- 1) The proportion of diabetic/non-diabetic patients with established cardiovascular disease, chronic kidney disease, or at high cardiovascular risk.
- 2) The proportion of diabetic patients with established cardiovascular disease, chronic kidney disease, or at high cardiovascular risk among all patients with diabetes;
- 3) The proportion of non-diabetic patients with established cardiovascular disease, chronic kidney disease, or at high cardiovascular risk among patients without diabetes;

Table 1. The proportion of patients with disease or risk among diabetic or non-diabetic patients

| | 2015 | | 2016 | | ... | | 2019 | | Overall | |
|--|-----------------|----------------|-----------------|----------------|-----------------|----------------|-----------------|----------------|-----------------|----------------|
| | Outpatie nts | Inpatient s | Outpatie nts | Inpatie nts | Outpatie nts | Inpatient s | Outpatie nts | Inpatient s | Outpatie nts | Inpatient s |
| | n (%) | n (%) |
| Patients diagnosed with diabetes | | | | | | | | | | |
| Group A (n, %) | | | | | | | | | | |
| with cardiovascular disease | | | | | | | | | | |
| with chronic kidney disease | | | | | | | | | | |
| at high cardiovascular risk | | | | | | | | | | |
| Patients diagnosed without diabetes | | | | | | | | | | |
| Group C (n, %) | | | | | | | | | | |
| with cardiovascular disease | | | | | | | | | | |
| with chronic kidney disease | | | | | | | | | | |
| at high cardiovascular risk | | | | | | | | | | |

Note: Group A: Diabetes with cardiovascular disease, chronic kidney disease or at high cardiovascular risk; Group B: Diabetes without cardiovascular disease, chronic kidney disease or at high cardiovascular risk; Group C: Non-diabetes with cardiovascular disease, chronic kidney disease or at high cardiovascular risk; Group D: Non-diabetes without cardiovascular disease, chronic kidney disease or at high cardiovascular risk;

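### The peripheral artery disease code list counts .5 codes under E10 and E14 but none under E11, so the diabetic cardiovascular row of Table 1 can miss patients

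*SAP*

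**What the plan says.** SAP 6.3 gives three routes into cardiovascular disease. Two are code ranges: "at least 1 discharged diagnosis or 2 outpatient diagnosis of ischemic heart diseases (ICD-10 I20~I25") and "at least 1 discharged diagnosis or 2 outpatient diagnosis of cerebrovascular diseases (ICD-10 I60~I69"). The third is a list of individual codes: "ischemic peripheral artery disease (ICD-10 E10.501, E11.603, E14.501, E14.606, E14.503, I73.9, I99.03, I99.04"). Protocol 9.2.2 has the same eight codes, "ICD-10 E10.501, E11.603, E14.501, E14.606, E14.503, I73.9, I99.03, I99.04", so this is not a copying slip in one document. Heart failure is a separate condition, outside the cardiovascular disease definition.

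The diabetic population is wider than the diabetes categories on that list: "patients with at least 1 discharged diagnosis or 2 outpatient diagnosis of diabetes (ICD-10 E10-E14"). Group B is the diabetic patients "but not with diagnosis of cardiovascular disease, heart failure, chronic kidney disease or at high cardiovascular risk".

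The second primary outcome in SAP 7.2.1 is "The proportion of diabetic patients with established cardiovascular disease, chronic kidney disease, or at high cardiovascular risk among all patients with diabetes". SAP Table 1 reports it through the Group A line and, beneath it, separate rows for cardiovascular disease, chronic kidney disease and high cardiovascular risk.

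Neither document labels the listed extensions, explains why the categories are treated differently, or plans a sensitivity analysis on the list.

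**The concern.** By listing them, the plan itself treats certain .5 extensions as ischemic peripheral artery disease when they stand under E10 or E14. It lists no .5 extension under E11. Followed as written, a complication in the same code position counts or does not count according to the diabetes category it was filed under.

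The cardiovascular row of Table 1 is at stake, and it belongs to the primary outcome. A patient who meets the one-discharge or two-outpatient rule on an E11 code is diabetic by definition, so the omission can lower only the diabetic row and never the non-diabetic one. It therefore pulls the diabetic versus non-diabetic contrast in one direction, and a larger database does not remove it.

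**Working it through.** **Step 1. Sort the list.** The eight codes, by parent category and first digit after the point:

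| Category | .5 codes listed | .6 codes listed |
|---|---|---|
| E10 | E10.501 | none |
| E11 | none | E11.603 |
| E12 | none | none |
| E13 | none | none |
| E14 | E14.501, E14.503 | E14.606 |

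The other three codes are I73.9, I99.03 and I99.04. E11 has a .6 entry and no .5 entry. E12 and E13 have no entry at all, although both are in the diabetes range.

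**Step 2. Who is missed.** To be missed in the cardiovascular row, a patient coded under E11 must hold the E11 counterpart of a listed .5 code and must have none of the following: E11.603, a listed E10 or E14 code, I73.9, I99.03, I99.04, I20 to I25, I60 to I69. To move from Group A to Group B, the same patient must also have no heart failure, chronic kidney disease, hypertension or hyperlipidemia.

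**Step 3. Size.** The plan states no figure to reproduce. Let f be the share of diabetic patients who meet the diagnosis rule on such an E11 code, and u the share of those with no other listed cardiovascular code. With all diabetic patients as denominator,

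shortfall in the cardiovascular row = f × u.

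Neither input is in the documents; both are assumptions.

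| f | u | Shortfall (points) | Patients per 100,000 diabetic patients |
|---|---|---|---|
| 1% | 10% | 0.1 | 100 |
| 5% | 30% | 1.5 | 1,500 |
| 10% | 60% | 6.0 | 6,000 |

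The shift in the combined Group A share is f × u × v, where v is the share of the missed patients with none of the four further conditions. Since v cannot exceed 1, the shift cannot exceed the shortfall, and it is smaller as soon as any missed patient has one of those conditions. The documents give no basis for a value of v.

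**Step 4. Compare with sampling error.** The standard error of a proportion near 50% is √(0.5 × 0.5 / n). It is 0.16 points for the 100,000 patients with full records in Protocol 9.5, and 0.065 points for all 600,000 diabetic patients. SAP 8 gives 10,000 patients with full records, for which it is 0.50 points. The low end of the range is of the order of sampling error or below it. The high end is far above it.

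**Step 5. Would the planned check find it?** Protocol 9.7.1 and SAP 11 plan a review of 200 random charts before analysis. Suppose, generously, that all 200 are diabetic patients. The chance that none is a missed case is (1 − f × u)^200:

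- shortfall 0.1%: 0.999^200 = 0.82
- shortfall 0.2%: 0.998^200 = 0.67
- shortfall 1.5%: 0.985^200 = 0.05

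The review would probably meet a case in the middle of the range but could easily meet none at the low end. Neither document states a rule for revising the list if a case is found. The checklist in Protocol Annex 2 answers No on analytic control of outcome misclassification (item 10.6). It answers Yes on sensitivity analyses (item 10.8), citing Protocol 9.7.1, which describes none.

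**The case against.** The strongest reply is that the extensions are local and unlabelled. E11.603 and E14.606 both stand on the list, so .6 extensions serve for peripheral artery disease here, and E11.603 may be this database's entry for that disease under E11. The authors also chose single extensions (E14.501 and E14.503, but not E14.502), which suggests deliberate selection. Nothing in the documents shows that E11 codes in the .5 position are used in this database.

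Much of this stands. It rules out any claim about the true size, and it means that the omission may prove to be intended. It does not close the matter. Under E14 the list carries a .6 code and two .5 codes together, so there the .6 entry did not make the .5 entries unnecessary. No reason is given why E11 should differ.

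A reader might infer more than the documents support:

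- **That patients coded under E11 with diabetic peripheral artery disease are counted as free of cardiovascular disease.** This is true only of those with none of the other qualifying codes in Step 2.
- **That the gap falls on type 2 diabetes.** The chart review in Protocol 9.7.1 does name "cardiovascular disease or at high cardiovascular risk, chronic kidney disease and type 2 diabetes", but neither document ties diabetes types to code categories, and the point does not need it.
- **That Group B and the second primary outcome are materially wrong.** Hypertension alone keeps a patient in Group A, and the documents do not allow the remaining shift to be sized.
- **That hospitals appear to differ because of how they code.** No comparison between hospitals is planned, and Protocol 9.9 already says that hospitals may understand the codes differently.

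**Conclusion.** The asymmetry is certain, present in both documents and unexplained. Its consequence for the cardiovascular row of Table 1 follows from the definitions, provided that E11 counterparts of the listed .5 codes are in use in the database. The direction is then known: the diabetic row is too low.

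The size is not known. The range of 0.1 to 6.0 percentage points rests wholly on the assumed 1% to 10% and 10% to 60%, and it applies to the cardiovascular row only. The effect on the combined Group A share and on Group B is smaller and cannot be given a figure. The point merits correction before analysis because the row is part of the primary outcome and the remedy is cheap. It is not evidence that the primary outcome as a whole is unsound.

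**What to change.** 1. Check the eight codes against the database's code dictionary and print their labels in SAP 6.3 and Protocol 9.2.2.
2. Add the E11 counterparts of the .5 extensions already listed (E11.501 and E11.503, or their local equivalents), and any E12 and E13 equivalents, in both documents. If the dictionary shows that E11.603 already covers the same complication and that no such E11 codes are in use, one sentence saying so is enough.
3. In Table 1, report the diabetic cardiovascular row with and without the added codes.

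The change should stay with the extensions the authors selected. Taking every .5 code by prefix would override their selection without the dictionary to justify it.

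The cost is one code-list edit in two documents and one extra table row. The added codes may bring in a few non-ischemic cases, and the two rows would show the most that this could amount to.
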